3.3 Number of patients

Up to 88 evaluable patients will be enrolled in the study.

The dose escalation portion of the study is completed. Dosed were 26 patients with advanced or recurrent solid tumors and 28 patients with recurrent or progressive GBM or high-grade glioma. In each of the groups 24 patients were evaluable for MTD assessment. Up to 34 evaluable patients with recurrent GBM whose tumor tissue is positive for EB1 and up to 6 evaluable patients with planned re-resection of recurrent GBM are expected to be treated in the expansion portion.

Assuming approximately 25% non-evaluability rate, up to 104 patients may be enrolled in total.

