- 2) Phase 2a expansion portion (Simon's two-stage design) to obtain efficacy data in patients with recurrent GBM whose tumor tissue is positive for EB1, and to further characterize the safety and tolerability of BAL101553 at the recommended Phase 2 dose (RP2D). A single-arm Simon's two-stage design will be used. The null hypothesis that the true objective response rate is 14% in patients with measurable disease at baseline will be tested against a one-sided alternative. In the first stage, 9 evaluable patients will be accrued. If there are 1 or fewer responses in these 9 evaluable patients, the study will be stopped. Otherwise, 10 additional evaluable patients will be accrued for a total of 19. The null hypothesis will be rejected if 6 or more responses are observed in 19 patients. This design yields a type I error rate of 3.7% and power of 81% when the true response rate is 40%. Patients with non-measurable disease at baseline will only contribute to the assessment of secondary endpoints.

Phase 2a expansion portion (Surgical cohort) – will be performed as a single-arm study if futility is rejected in Stage 1 of the Simon's two-stage study portion, and includes 6 patients with planned re-resection of recurrent GBM to determine brain tumor tissue levels of BAL27862. Details of this Surgical cohort will be provided in a separate protocol amendment.

Note: For changes to patient-related study procedures in response to the COVID-19 pandemic, see Section 5.2.

PLANNED NUMBER OF PATIENTS

- Phase 1 dose escalation portion (enrollment completed): 26 patients with advanced or recurrent solid tumors and 28 patients with recurrent or progressive GBM or high-grade glioma.
- Phase 2a expansion portion (Simon's two-stage design): Up to 34 evaluable patients with recurrent GBM whose tumor tissue is positive for EB1. This includes up to 19 patients with measurable disease and up to 15 patients with non-measurable disease at baseline.
- Phase 2a expansion portion (Surgical cohort): 6 evaluable patients with planned re-resection of recurrent GBM to determine brain tumor tissue levels of BAL27862.

NUMBER OF CENTERS/LOCATIONS

- Phase 1 dose escalation portion (enrollment completed): 2 6 study centers in the UK
- Phase 2a dose expansion portion (Simon's two-stage design): Up to 20 study centers in the UK, Switzerland, Germany, and potentially other countries

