3.1.1 Treatment cycles

Each treatment cycle will comprise 28 days of continuous, daily oral BAL101553 administration to patients in a fasted state. Section 3.2.6 describes the planned treatment duration.

Treatment may be administered on an inpatient or outpatient basis.

In the Phase 1 dose-escalation portion of the study, patients will be replaced if the minimum safety evaluation requirements for assessment of the MTD in Cycle 1 have not been met (see Sections 3.1.2 and 4.5).

In the Phase 2a dose expansion portion of the study, patients with measurable disease at baseline will be replaced if they could not complete at least one post-baseline RANO assessment after at least 6 weeks of study treatment (see Sections 3.1.3 and 4.5).

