3.1.3 Expansion portion (Phase 2a)

Once the MTD has been defined, additional patients will be enrolled and treated at the RP2D dose of 25 mg/day (see Section 1.5.4). Enrolled patients will be evaluated for safety, pharmacokinetics, pharmacodynamic effects, and for antitumor activity.

At a minimum, a cumulative safety evaluation will be performed at the time of stage transition (see Section 8.3.2) and after approximately, 5 and 15 patients of the Simon's two-stage design have completed their first 28-day cycle, or have discontinued treatment. These evaluations will be performed by a committee comprising a minimum of:

- The Co-ordinating Investigators or delegates of each country
- The Sponsor's Project Physician (or qualified delegate)
- An external/independent cardiologist

Detailed information regarding committee composition, processes, and decisions will be provided in the Safety Evaluation Charter.

Patients who withdraw prior to their post-baseline RANO assessment after having received at least 6 weeks of study treatment will be replaced by enrollment of additional patients (see Section 3.2.6 and Section 4.5).

BAL101553 treatment will be continued in patients enrolled in the dose expansion portion until disease progression, occurrence of unacceptable toxicity or until the patient withdraws from the study (see Section 4.4). Efficacy assessments to assess response to treatment must be scheduled at the end of at least each even-numbered treatment cycle (e.g., end of

Cycle 2, 4, 6, etc.) and subsequent treatment cycles may not be initiated if disease progression is observed. Patients with a mixed response, e.g. a reduction in target lesion area but an increase in non-target disease or occurrence of new lesions, may continue on study treatment if their clinical condition is stable or improving. From Cycle 6 onwards, the interval between MRI scans may be extended from 8 weeks to 12 weeks. Section 5.6 provides criteria for assessing response, stable disease, and disease progression.

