4.5 Replacement of patients

Patients in the dose escalation portion of the study (Section 3.1.2) must meet the following minimum safety evaluation requirements in Cycle 1:

- Received at least one dose of BAL101553 and experienced a DLT.
- Received at least 24 of the scheduled 28 doses of BAL101553 for q24h administration, or at least 48 of the scheduled 56 doses of BAL101553 for q12h administration, without experiencing a DLT (including the ability to initiate treatment Cycle 2), have been observed for ≥ 28 days following the first dose, and have been evaluated for safety.

BAL101553 Clinical Study Protocol CDI-CS-002

Version 11.0 1 July 2021, page 61 of 135

The correct dose must be given as described in Section 6.5.

Patients who do not meet these minimum requirements in the dose escalation portion of the study will be replaced by recruitment of new patients.

In the Phase 2a dose expansion portion of the study (Simon's two-stage design, see Section 3.1.3), patients with measurable disease at baseline who discontinue the study treatment will be replaced if they did not have at least one postbaseline RANO assessment after having received at least 6 weeks of study treatment.

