5.3 Summary of study visits

5.3.1 Screening visit

Informed consent must be obtained within the 28 days prior to administration of the first dose of study drug.

Patients must provide written informed consent before any screening-specific assessments are performed. Study centers must maintain a log of all consenting patients, which must include date and time of consent.

Screening assessments must be performed in accordance with Table 8 or Table 9. Screening must be initiated and completed within the 15 days prior to Day 1 of Phase 1 Cycle 1 (except for certain radiology assessments, which may be obtained within the 35 days prior to Day 1).

Patients will be assigned a subject number once they have provided consent. Patients are considered to be enrolled in the study once it is confirmed that they meet all of the eligibility criteria for the study.

Abnormal findings from the physical examination must be recorded (see Section 5.5.3). Body weight and height must also be recorded.

Vital signs and ECG must be performed as described in Sections 5.5.4 and 5.5.5.

BP measurements should be obtained as described in Section 5.5.4.3 and Table 10.

Transthoracic echocardiography must be performed as described in Section 5.5.6.

Laboratory safety tests (hematology, biochemistry, coagulation, cardiac troponin and urinalysis) must be assessed as described in Section 5.5.7.

Women of child-bearing potential must have a negative serum pregnancy test (hCG) conducted at screening, as described in Section 5.5.7.6 (see also Section 7.3).

Procedures for obtaining and handling blood samples and archival tumor specimens are described in Sections 5.8.1 and 5.8.3, respectively. If a tumor biopsy is taken in Phase 1 (if easily accessible and deemed safe for the patient by the Investigator and if patients are willing to undergo biopsy, see Section 5.8.1.1), the blood samples for biomarker analysis should be obtained prior to tumor biopsy.

The assessment of cancer and the selection and reporting of radiological marker lesions or other assessment endpoints (CA-125 or PSA) are described in Section 5.6.

A chest X-ray (or chest CT scan) must be performed in patients in the Phase 1 portion of the study to establish a baseline for safety assessments and will be repeated as clinically indicated. For tumor assessments, a chest CT scan should be performed. When a chest-CT scan is performed, a chest X-ray is not required (see Section 5.6).

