8.3.1.4 Pharmacokinetic analysis population

The PK analysis set includes all patients who received at least one dose of study drug and had at least one post-baseline pharmacokinetic assessment.

8.3.1.5 Efficacy-evaluable population (Phase 2a expansion portion of the study, Simon's two-stage design)

The efficacy evaluable population (EEP) is the subset of the FAP who had at least one postbaseline RANO assessment after having received at least 6 weeks of study treatment.

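### Does the enrolment ceiling of 104 in Protocol Section 3.3 contradict its assumed 25% non-evaluability?

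*Protocol*

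**What the plan says.** Section 3.3 of the protocol sets two totals. The first is "Up to 88 evaluable patients will be enrolled in the study". It is made up of 24 evaluable patients in each of the two completed Phase 1 groups, up to 34 in the Simon two-stage part and up to 6 in the surgical cohort. The second is the enrolment ceiling: "Assuming approximately 25% non-evaluability rate, up to 104 patients may be enrolled in total". The calculation behind the ceiling is not shown. Section 8.3.3.2 sends the reader to Section 3.3 for actual patient numbers.

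The synopsis splits the 34: "This includes up to 19 patients with measurable disease and up to 15 patients with non-measurable disease at baseline". Section 5.3.1 defines enrolment: "Patients are considered to be enrolled in the study once it is confirmed that they meet all of the eligibility criteria for the study". Section 8.3.1.5 defines the efficacy-evaluable population (EEP), which "is the subset of the FAP who had at least one postbaseline RANO assessment after having received at least 6 weeks of study treatment".

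On replacement, Section 4.5 says that "patients with measurable disease at baseline who discontinue the study treatment will be replaced" if they lack a qualifying RANO assessment, and Section 3.1.1 carries the same limit ("patients with measurable disease at baseline will be replaced if they could not complete at least one post-baseline RANO assessment"). Section 3.1.3 is worded without it: "Patients who withdraw prior to their post-baseline RANO assessment after having received at least 6 weeks of study treatment will be replaced by enrollment". Section 3.2.6 also omits it. Both of these sections refer the reader to Section 4.5. The SAP repeats the limited wording in Section 3.3.1 and the unlimited wording in Sections 3.3.1.2 and 3.3.2.

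**The concern.** A non-evaluability rate is normally a share of the patients enrolled. On that meaning, 25% and 104 do not match over the whole expansion portion: 50 places for 40 evaluable patients is 20%. Dividing by 0.75 gives 54 places and a total of 108. The usual slip of multiplying by one plus the rate, where one should divide by one minus the rate, would explain the printed figure.

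The two forms of the replacement rule add to the doubt, because the ceiling depends on whether the 15 patients with non-measurable disease are to be topped up to 15 evaluable. What would be at stake is a ceiling set a few places too low, so that the trial could run out of places before it had its evaluable patients.

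**Working it through.** **Inputs** (Section 3.3 and synopsis): Phase 1 dosed 26 + 28 = 54; Phase 1 evaluable 24 + 24 = 48; Simon part 34 = 19 measurable + 15 non-measurable; surgical cohort 6; rate about 25%; ceiling 104.

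**Evaluable total.** 48 + 34 + 6 = 88, as printed.

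**Places left for the expansion portion.** 104 - 54 = 50, for 34 + 6 = 40 evaluable. The ten spare places are 10/50 = 20% of those enrolled and 10/40 = 25% of the evaluable target.

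**Reproducing 104.** 54 + 40 x 1.25 = 54 + 50 = 104, an exact match. This derivation is inferred; the protocol does not print it.

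**25% read as a share of enrolled**, each cohort rounded up: 34/0.75 gives 46, 19/0.75 gives 26, 6/0.75 gives 8.

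| Cohorts to which 25% applies | Expansion places | Total |
|---|---|---|
| All 40 | 46 + 8 = 54 | 108 |
| Simon part only | 46 + 6 = 52 | 106 |
| Measurable disease and surgical | 26 + 15 + 8 = 49 | 103 |
| Measurable disease only | 26 + 15 + 6 = 47 | 101 |

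The last two rows follow Section 4.5, under which only measurable-disease patients in the Simon part are replaced. Both lie below 104. The first row inflates the 15 non-measurable patients, whom Section 4.5 does not replace, and the surgical cohort, whose details are left to a separate amendment.

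**Does the ceiling leave room for the primary analysis?** Taking 15 non-measurable and 6 surgical places from the 50 leaves 50 - 21 = 29 for measurable disease. At 25% loss the expected yield is 29 x 0.75 = 21.75, against the 19 needed. With 8 surgical places it is 27 x 0.75 = 20.25. With 29 places, 19 evaluable allows a loss of up to 10/29 = 34.5%. These are expected counts, so chance could use up more places.

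**Simon design.** Go on if at least 2 of 9 respond, reject if at least 6 of 19 respond. Exact binomial sums give a type I error of 0.0371 at 14% and a power of 0.813 at 40%, matching the stated 3.7% and 81%. The chance of stopping after stage 1 at a true rate of 14% is 0.86^9 + 9 x 0.14 x 0.86^8 = 0.634. Enrolment totals do not enter any of these.

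**The case for a change.** The strongest counter-argument is that an exact match obtained with the wrong formula explains the discrepancy without removing it. The text calls 25% a rate, and a mark-up on the target is not a rate of non-evaluability. None of the four share-of-enrolled readings gives exactly 50 places; they give 54, 52, 49 and 47. The 54 Phase 1 patients are fixed, so the comparison should be made against 50 and not 104. Places are also costly here: Section 1.5.2.2.2 expects 25 to 50 tissues to be screened per EB1-positive case, so four Simon places would mean 100 to 200 tissues. Finally, under Section 4.5 the 15 non-measurable patients would be expected to give 15 x 0.75 = 11.25 in the EEP, so 19 + 11.25 = 30.25 against 34.

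It stands that Section 3.3 leaves the base and the cohorts unstated, and that the replacement wording is looser in Protocol 3.1.3 and 3.2.6 and in SAP 3.3.1.2 and 3.3.2. The rest carries little weight. The section says approximately, and gives a maximum, so a reading that falls below 104 is consistent with it. If all ten spare places went to the Simon part, the share would be 10/44 = 22.7%, which is near the stated figure. An expected 30.25 does not breach a target worded as a maximum of 34, and the 15 contribute only to secondary endpoints; OS and PFS are analysed in the FAP as well as the EEP. In the protocol, the looser replacement sentences point to Section 4.5, which settles the rule. The two SAP sentences lack that pointer, but SAP Section 4.6 bases response rate and stage transition on measurable-disease patients in the EEP.

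**Conclusion.** This is a missing detail that a reader can fill from the document's own numbers, and no change to the plan follows. The 25% is most simply read as an allowance over the 40 evaluable expansion patients, equivalent to 20% of the 50 places. Readings of 25% as a share of enrolled run from 101 to 108, and those that follow Section 4.5 (101 to 103) fit under the ceiling. The largest shortfall, four places, needs the rate to be applied both to patients who are not replaced and to a cohort not yet specified.

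Followed as written, the trial still seeks 19 evaluable measurable-disease patients, with the same boundaries, error rate, power and primary population. Raising the ceiling to 108 would be the only alteration with an effect on conduct; it would permit more enrolment without a gain for the primary question. The conclusion assumes that Section 4.5 governs replacement and that the inferred derivation of 104 is the one intended. If a later amendment touches Section 3.3, the base could be stated in passing, but nothing depends on it.

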3.4 Study centers

Four investigational centers participated in the dose escalation portion designed to characterize the MTD, and up to twenty investigational centers will participate in the expansion portion in patients treated at the RP2D.

4 STUDY POPULATION

4.1 Target population

Consenting patients with histologically or cytologically confirmed advanced or recurrent solid tumors who failed standard therapy, or for whom no effective standard therapy is available (Phase 1); or with recurrent or progressive GBM or high-grade glioma (Phase 1); or recurrent GBM with tumor tissue positive for EB1 (Phase 2a); or with planned reresection of recurrent GBM (Phase 2a); who meet the inclusion/exclusion criteria, will be eligible for enrollment into the study.

4.2 Inclusion criteria

Patients meeting all of the following inclusion criteria at screening will be eligible for enrollment in the study. Informed consent must be obtained within 28 days prior to the start of treatment. Screening evaluations will be performed within 15 days prior to start of treatment.

- 1. Age 18 years or older.
- 2. Patients who have in the:

Phase 1 dose escalation portion either of the following:

- a. a histologically- or cytologically confirmed advanced or recurrent solid tumor, who failed standard therapy, or for whom no effective standard therapy is available to them*
- b. histologically-confirmed GBM or high-grade glioma, with progressive or recurrent disease after prior radiotherapy, with or without chemotherapy. This will also include patients with histologically-confirmed low-grade glioma who present with unequivocal evidence by imaging of transformation to high-grade glioma/GBM.
- * Patients with brain metastases must have undergone definitive treatment (surgery and/or radiation) at least 3 months prior to starting study drug and be documented as having stable disease by imaging.

Phase 2a dose expansion portion (Simon's two-stage design):

Recurrent, histologically confirmed, GBM with tumor tissue positive for EB1 by IHC as determined by central laboratory testing; eligible are patients with de novo GBM after prior radical chemoradiotherapy or secondary GBM after prior chemotherapy or radiotherapy; patients must be neurologically stable, without progression of neurologic symptoms, within 15 days prior to starting study drug.

Phase 2a dose expansion portion (Surgical cohort):

Recurrent GBM with planned re-resection. Details of the inclusion criteria for the Surgical cohort will be provided in a separate protocol amendment if futility is rejected in Stage 1 of the Simon's two-stage study portion.

3. Phase 1 dose escalation portion

Patients with advanced solid tumors must have measurable disease (according to Response Evaluation Criteria in Solid Tumors [RECIST] v1.1) documented within 35 days prior to starting study drug, or non-measurable prostate or ovarian cancer that can

be followed by prostate specific antigen (PSA) or cancer antigen-125 (CA-125), documented within 15 days prior to starting study drug.

Patients with glioblastoma or high-grade glioma must have measurable disease, defined by contrast-enhancing MRI, within 15 days prior to starting study drug. Patients with previous low-grade glioma that progressed after prior radiotherapy (with or without chemotherapy) and are found to have high-grade glioma/GBM by biopsy or imaging are also eligible.

Phase 2a dose expansion portion (Simon's two-stage design):

Patients with recurrent glioblastoma must be evaluable per RANO, defined by contrast-enhancing MRI, within 15 days prior to starting study drug.

- 4. Life expectancy ≥ 12 weeks.
- 5. Acceptable organ and marrow function documented within 15 days prior to starting study drug, defined as follows:
 - Absolute neutrophil count $\geq 1.5 \times 10^9/L$.
 - Platelets $\geq 100 \times 10^9/L$.
 - Hemoglobin ≥ 9 g/dL.
 - Total bilirubin ≤ 1.5 × institutional upper limit of normal (ULN), unless the patient has known Gilbert's syndrome.
 - Aspartate amino transferase (AST) and alanine amino transferase (ALT) $\leq 2.5 \times \text{institutional ULN or} \leq 5 \times \text{ULN in presence of liver metastasis.}$
 - Serum creatinine ≤ 1.5 × institutional ULN, or creatinine clearance ≥ 60 mL/min by Cockcroft-Gault formula.
 - Serum sodium \geq the institutional lower limit of normal (LLN).
 - *All listed laboratory parameters, and cardiac troponin (see Exclusion criterion 13), must be included in the study-specific pharmacy prescription chart. During the study, all parameters applicable for any study visit must be reviewed by the investigator and the pharmacy prior to dispensing of any study medication.
- 6. Patients with advanced solid tumors must have an Eastern Cooperative Oncology Group (ECOG) performance status ≤ 1 and patients with recurrent or progressive glioblastoma must have an Eastern Cooperative Oncology Group (ECOG) performance status ≤ 2.
- 7. Female patients who are not pregnant or breast-feeding and meet one of the following conditions:
 - Postmenopausal defined as at least 12 months with no menses without an alternative medical cause; in women < 45 years of age a high follicle stimulating hormone (FSH) level in the postmenopausal range may be used to confirm a postmenopausal state in women not using hormonal contraception or hormonal replacement therapy. In the absence of 12 months of amenorrhea, a single FSH measurement is not sufficient.
 - Post-hysterectomy and/or post-bilateral salpingectomy or ovariectomy.
 - Congenital or acquired condition that prevents childbearing.

- Women of childbearing potential must have a negative serum human chorionic gonadotropin (hCG) pregnancy test result and must use highly effective contraceptive methods for the duration of the study and for an additional 90 days after the last dose of study drug. Highly effective contraceptive methods include:
 - male or female sterilization (bilateral tubal occlusion or vasectomy)
 - intrauterine device (IUD)
 - intrauterine hormone-releasing system (IUS)
 - combined (estrogen and progestogen containing) hormonal contraception associated with inhibition of ovulation (oral, intravaginal, transdermal)*
 - progestogen-only hormonal contraception associated with inhibition of ovulation (oral, injectable, implantable)*
 - total heterosexual abstinence
 - * The hormonal contraception method must be supplemented with a barrier method (preferably male condom).
- 8. Male patients must agree not to donate sperm from the first dose of study drug until 90 days after the end of treatment. Male patients, without a vasectomy or other conditions resulting in azoospermia and with a partner of childbearing potential, must agree to use condoms during the study and for at least 90 days after the end of treatment. The patient should be instructed that their female partner should use another form of contraception for the duration of the study and continue this use for at least 90 days after the last dose of study drug.
- 9. Signed, written informed consent must be obtained and documented according to the International Conference on Harmonization's Guideline for Good Clinical Practice E6 (ICH-GCP), the local regulatory requirements, and the permission to use private health information in accordance with the Health Insurance Portability and Accountability Act (HIPAA), where required, prior to study-specific screening procedures.
- 10. Patients must be able and willing to comply with the required food intake restrictions.

